## **Section 2.8 Intervention Group Instructions**

If the participant was assigned to the intervention group, the following tasks need to be completed before they leave the appointment:

1) Give the participant the Fitbit®.

2) Help the participant create a Fitbit® account by having them download the Fitbit® app from their app store and follow these steps:

- 1) Make sure their phone’s Bluetooth is turned on.
- 2) Once the app is downloaded, open the app and click ‘Join Fitbit’.

- 3) Choose 'Charge 3' as the Fitbit Tracker.
- 4) Click 'Set Up Your Fitbit Charge 3'
- 5) Click 'Let's Go'
- 6) Have them scroll up or down to their current height. Click 'Next'.
- 7) Select their gender by clicking on the appropriate picture. Click 'Next'.
- 8) Have them scroll left or right to their current weight. Click 'Next'.
- 9) Have them scroll left and right to input their birth date. Click 'Next'.
- 10) Have them enter their Full Name, Email Address, and Password. They will need to agree to the Terms of Service and Privacy Policy by clicking the check mark. Let them choose if they would like to receive news and promotions from the company.
- 11) Click 'Next' to get past the Terms of Service and Privacy Policy screen.
- 12) Let them Meet their Charge 3 by clicking 'Next' through the tutorial page.
- 13) You may need to plug the Charge 3 in to complete set up.
- 14) Make sure the Charge 3 is awake and close to the phone so that they can sync.
- 15) Once it syncs, it will ask for the 4-digit number of the Fitbit screen.
- 16) Click 'Next' and 'Done' to get through some tutorial information.
- 17) They will then be logged into the Fitbit app. They may have a warning that email verification is required. They can do this at a later time.
- 18) Show them that steps, distance, calories, and minutes of exercise are tracked on the dashboard.

- 3) Enroll the participant in MapTrek by visiting <https://vinci.cs.uiowa.edu/maptrek2/admin/>

- o Log in using your username and password
- o Basic Strategy: start at the bottom of the screen and work your way up
- o On the Home Screen, right click on the 'Change' next to Player Icons, choose 'Open link in new tab'
- o Using the 4 categories (animals, military, outdoors, other), help the participant choose an icon
- o Navigate back to MapTrek and click 'Add' next to 'Players'
- o Have the participant choose a username (**Note:** inform them that this username will be visible by others, so they should make it something that is non-identifiable if they wish!)
- o Enter the participant's phone number
- o Have the participant choose the earliest and latest times that they wish to receive text messages
- o Use the Notes field for any information you may want to remember about the person (that is not HIPAA sensitive)
- o Choose the requested icon from the dropdown menu
- o Click 'Save'
- o Click 'Add' next to League Participants
- o Choose the player from the dropdown menu
- o Choose the VA FY19-20 Intervention league from the dropdown
- o Make sure 'Active' is not selected
- o Click 'Save'

- Click on the words ‘User fitbits’
- Click on ‘Associate New User Fitbit’ in the top right corner
- Choose the participant from the dropdown menu, click ‘Authentic with Fitbit’
- You will be taken to the Fitbit® screen and asked to provide the participant’s Fitbit login information. Once they have entered their email and password, you need to select “Allow All” from the dropdown menu and click Allow. Once this is completed, their Fitbit will be synced with MapTrek

4) Give the participant the MapTrek Instruction Packet (Appendix D). Talk through each slide of the instructions and answer any questions that the participant has.

5) Have the participant put the Fitbit® on now and instruct them to continue wearing it every day until the 9 weeks are finished (unless they are bathing, swimming, or sleeping).

6) Remind them they will receive either a text message or a phone call to complete the exit survey at the end of the study.

Once these tasks have been completed, the participant is free to leave.

### **Section 2.9 Data Entry Procedures**

Once the participant has left, you need to complete 3 REDCap surveys- Baseline Participant Info (Appendix E), Baseline Medications (Appendix F), and Baseline Comorbidities (Appendix G). The necessary information will come from your discussion with the participant and CPRS.

### **Section 2.10 Storing the Files**

When you are done working in the clinic for the day, all of the participant informed consent forms/HIPAA authorization forms must be taken to the annex at UIHC to be stored in the locked cabinets.

**Note:** Be sure you have your Authorization to Transport form with you before you transport any forms off of the VA campus!

### **Section 2.11 Submitting Payments**

Once a participant has completed the exit survey, they need to be compensated. Open the PaymentTemplate\_MapTrekFitbitGame file using the following path: rdss\_Ipolgree > MapTrek Pilot > FitbitGame > Payments.

Create a new file by clicking “Save As” and re-naming the file using the following the date the payment was submitted to eVouchers (example: 01.29.2019.xlsx).

Complete the spreadsheet by copying and pasting the participant’s information from the ParticipantInfo\_MapTrekFitbitGame spreadsheet. You can include multiple participants in this spreadsheet before submitting.

Instructions on how to submit the payment are found in Payment Procedures file listed under rdss\_Ipolgree > MapTrek Pilot > FitbitGame > Payments.

## Appendices

## Appendix A

**Screening Survey**

Invitation status: [Survey options](#)

**Editing existing Record ID 1**

Event Name: **Screening**

|   |   |
|---|---|
| Record ID   | 1   |
| 1. Are you comfortable speaking and reading in English  |  Yes
 No
<small>If no, ineligible</small>             |
| 2. What is your current age?  | 
<small>Participants younger than 18 or older than 100 are ineligible.</small> |
| 3. Do you own a smartphone with text messaging and internet capabilities?   |  Yes
 No
<small>If no, ineligible</small>             |
| 4. Do you already have a Fitbit account?  |  Yes
 No   |
| 5. Are you male or female?  |  Male
 Female  |
| 6. What is your current height (in)?  |   |
| For office use only: Date height was measured/reported  |   M-D-Y                                       |
| 7. What is your current weight (lb)?  |   |
| For office use only: Date weight was measured/reported  |   M-D-Y                                       |
| Calculated BMI  |  View equation
<small>if < 25, ineligible</small>           |
| 8. If you are enrolled in the study, would you prefer your exit survey via a text message or phone call?                              |  Text message
 Phone call                                |
| For office use only: Were height/weight/BMI self-reported or from CPRS?   |  Self-reported
 CPRS                                     |
| For office use only: Is the participant eligible?   |  Yes
 No   |
| For office use only: Randomized to intervention or control?   |  Control
 Intervention                                   |
| For office use only:  |   |
| Notes:  |   |
| Expand  |   |
| Form Status  |   |
| Complete?   |                                         |
| Lock this record for this form?  |   |
| <small>If locked, no user will be able to edit this record on this form until someone with Lock/Unlock privileges unlocks it.</small> |   |
|    |   |
|   -- Cancel --       |   |

## Appendix D

The image is divided into two main sections. The left section is a teal-colored card with the white text "GET STARTED" and a white walking person icon inside a light blue teardrop marker. The right section shows a smartphone displaying a text message. The message reads: "Hi [name], respond to this message to confirm your phone number for study MapTrek: 4 Week Pilot." Below the phone is a text block: "Before the start of the 1st race, you'll get a text message asking you to confirm your phone number." At the bottom, it says "Reply 'OK' to confirm your phone number." A small number "2" is in the bottom right corner of the right section.

GET STARTED

Before the start of the 1st race, you'll get a text message asking you to confirm your phone number.

Reply "OK" to confirm your phone number.

2

## GET STARTED

On the 1st day of every race, you'll get a text message with a link to the route's location.

Throughout the race, you may receive additional messages if you forget to sync or wear your Fitbit®.

3

## SYNCING YOUR FITBIT:

At least once per day, open the Fitbit® app on your phone and drag the screen down. This will sync your Fitbit® to the app and advance your character along the route.

**Tip:** Turn on “all-day sync” in the Fitbit® app on your phone, this will also help keep your progress along the route current.

4

## THE RACE

## GET MOVING

Steps recorded by your Fitbit® will move your character along a route on a map.

During the race, you will receive daily text messages.

Click the link in the text messages to display the following features:

The Route Leaderboard Street View

5

## THE ROUTE

The route is indicated by a line on the map.

[figure not shown]
You are represented by an icon and your chosen username.

You can zoom in and out on the map to see other players' locations along the route.

6

[figure not shown]
## LEADER BOARD

- 1
- 2
- 3

## LEADER BOARD

- 1
- 2
- 3

## RACE CHALLENGES

You may periodically receive challenges.

A fulfilled challenge will move your character along the route by the number of bonus steps awarded.

9

## MAPTREK NOTES

If you have any questions or problems throughout the study, text “Support” with a brief description of your problem and we will contact you ASAP.

In the unlikely event that you wish to immediately stop receiving communication from MapTrek, text “Support” followed by a separate text message with only the word “Stop”.

10

## Appendix E

### Baseline Participant Info

Editing existing Record ID 1

Event Name: **Baseline**

|   |   |
|---|---|
| Record ID   | 1   |
| First name  |   |
| Last name   |   |
| Last 4 SS   |   |
| Race  |  American Indian or Alaskan Native
 Asian
 Black or African American
 Native Hawaiian or Other Pacific Islander
 White
 Declined/Unknown |
| Ethnicity   |  Not hispanic/latinx
 Hispanic/latinx  |
| Marital status  |  Divorced
 Married
 Never married
 Separated
 Single
 Widowed
 Unknown
 Other            |
| Systolic blood pressure   |   |
| Date SBP was measured   |  M-D-Y  |
| Diastolic blood pressure  |   |
| Date DBP was measured   |  M-D-Y  |
| Zipcode   |   |
| Urban/Rural   |  Rural
 Urban  |
| Will be determined with help from [name]  |   |
| Form Status   |   |
| Complete?   |    |
| Lock this record for this form?
If locked, no user will be able to edit this record on this form until someone with Lock/Unlock privileges unlocks it. |   |
|    |   |
|    |   |
|    |   |

## Appendix F

### Baseline Medications

Current instance:

6

 Editing existing Record ID 1 (Instance #6)

|  |  |
|--|--|
| Event Name: Baseline  |  |
| Record ID  | 1  |
| Medications  |    |
| Form Status  |  |
| Complete?  |            |
| Lock this record for this form?
If locked, no user will be able to edit this record on this form until someone with Lock/Unlock privileges unlocks it. |  |
|   Lock   |  |
|        |  |

[figure not shown]

## Appendix G

 **Baseline Comorbidities**

Current instance: 4

 **Editing existing Record ID 1 (Instance #4)**

|  |  |
|--|--|
| Event Name:  | Baseline  |
| Record ID  | 1  |
| Comorbidities  |    |
| Form Status  |  |
| Complete?  |   Incomplete ▾        |
| Lock this record for this form?
If locked, no user will be able to edit this record on this form until someone with Lock/Unlock privileges unlocks it.   |  |
|   Lock   |  |
| Save & Exit Form Save & Add New Instance ▾ |  |
| -- Cancel --   |  |

VA MapTrek- Yr 2

IRB #: 201901762

Statistical Analysis Plan

Creation Date: 6/7/2024

VA MapTrek **Statistical Analysis Plan**

We only used data from after the start of the intervention in our analysis; the baseline data was not used to estimate the model. We defined the start date of the intervention as Day 0 for all participants.

Statistical analysis was done using Bayesian mixed effects linear regression. We included fixed effects for day-of-week, days since the start of the intervention period, group indicator (Intervention Group versus Control Group), and an interaction between group and days since intervention period start. We included two random effects: random intercept and random slope by participant. The random effects were modeled using a bivariate normal distribution.

We included vague priors on all parameters. All model fixed effects had priors of $U(-\infty, +\infty)$. We imposed slightly limited priors on the standard deviation of step counts within a person and the on-diagonal values of the covariance matrix for the random effects of $U(0, 25,000)$. This upper bound of 25,000 was at 4-5x greater than the largest plausible values for these values and was set to accelerate sampling. The off-diagonal elements of the covariance matrix were given a Lewandowski, Kurowicka, and Joe prior with a shape parameter of 2. Our prior belief is that the random slope and intercept values will be correlated but we are very uncertain about the extent of that correlation. A shape parameter of two provides a weak prior in favor of correlation.

We estimated the model using Bayesian Hamiltonian Monte Carlo (HMC) simulation using Stan No-U-Turns sampler (NUTs). We ran 6 chains for 25,000 draws on each chain. We discarded the first 5,000 draws as burn-in and assumed the remaining 20,000 draws per chain reflected the posterior equilibrium. More convergence was assessed using \check{R} , effective sample size, and the Monte Carlo error relative to the total parameter error.

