## Section 1.2 Research Questions

The purpose of the proposed project is to contribute to and improve upon the existing weight management and physical-activity-promoting programs available to veterans. Our specific objectives are to:

- 1) Assess the effectiveness of VA MapTrek as a whole to increase steps per day in veterans compared to the control group.
- 2) Assess the effectiveness of challenges within VA MapTrek to increase steps per day in veterans in the intervention group.
- 3) Identify additional areas of development within the MapTrek program to improve its future efficacy among veterans.

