## Section 1.3 Project Outline

All consented participants will be provided with a Fitbit and instructed to wear it all day, every day for the next 9 weeks (The first few participants may require an additional week or two of wear as we will not begin the first MapTrek race until we have at least 5 participants enrolled in the study. They will be told this upon enrollment.). We expect the enrollment process to take anywhere from 15 to 45 minutes, depending on group assignment and participant familiarity with using Fitbits.

This, plus an exit survey (given via text message or phone, whichever the participant prefers), will be the extent of participation for the control group.

Members of the intervention group will be instructed on how to use MapTrek, our virtual walking race, and will also be given an instruction packet to refer to later. Data collected during the first week from the Fitbit will be used to compute baseline activity level. This baseline data will be used to place participants into an appropriate initial race group. Participants are placed into groups with other individuals who are active at a similar level, so that groups will be competitive.

Each virtual walking race will begin on Monday morning and end on Saturday night. Results of each race will be announced on Sundays. Depending on their performance each week, group assignment may change. Participants will compete in 8 week-long races over the course of the study.

Participants will receive 2-4 text messages per day including a daily status report and a link to view the race. They will also periodically receive challenge messages. If a participant completes a challenge, they will be awarded bonus steps to help move them along the route quicker.

To win a race, a participant must be furthest along on the route at 11:59 pm on Saturday. There is a leaderboard within MapTrek that helps participants determine their standing within each race. Participants are allowed to choose the screen name displayed on the leaderboard so that they may remain anonymous if desired.

At baseline, we will collect the following data about all participants: first and last name, last 4 of social security number (for consent documentation and to look up records in CPRS), age, sex, race,

ethnicity, marital status, height, weight, body mass index, blood pressure, zip code, current medications, and comorbidities.

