- Enter the Record ID for the participant from REDCap as the subject identifier (you do not need to enter an email address, Preferred Language should be kept as English for this study)
- Select “Go to registration page” and click Submit
- You will be taken to the Fitbit® screen and asked to provide the participant’s Fitbit login information. Once they have entered their email and password, you need to select “Allow All” from the dropdown menu and click Allow. Once this is completed, their Fitbit will be synced with Boomerang
- Return to Boomerang, Click on the Patients tab, and select the Record ID for the patient you just enrolled
- Click the Green “Add Subscription” button in the top right corner
- Select “Fitbit Reminders” as the Protocol, “Today” as the start date, the Saturday date following the end of their 9 weeks of participation as the End Date, Frequency should be set to “1”, allow the participant to choose the times they will receive reminders to wear-sync their Fitbit, uncheck both “Send end message” and “Send end email to managers”, and click Submit
- From the home screen in Boomerang, make sure the subscription worked by clicking the Patients tab, selecting the patient, and clicking on the Subscriptions tab. Make sure the subscription is set up correctly

4) Have the participant put the Fitbit® on now and instruct them to continue wearing it every day until the 9 weeks are finished (unless they are bathing, swimming, or sleeping).

5) Remind them they will receive either a text message or a phone call to complete the exit survey at the end of the study.

Once these tasks have been completed, the participant is free to leave.

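### Could a difference in Fitbit wear between arms be read as a walking effect, because the SAP gives no rule for zero, unsynced or part-worn days?

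*SAP*

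**What the plan says.** The first objective in Protocol Section 1.2 is to "Assess the effectiveness of VA MapTrek as a whole to increase steps per day in veterans compared to the control group". Steps are counted by a Fitbit.

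The SAP is one page and describes an analysis already carried out. "Statistical analysis was done using Bayesian mixed effects linear regression", it says, and the one stated restriction on the data is "We only used data from after the start of the intervention in our analysis". On the model: "We included fixed effects for day-of-week, days since the start of the intervention period, group indicator", with a group-by-day interaction; and "We included two random effects: random intercept and random slope by participant". Neither document gives a valid-day definition, a rule for zero-step or unsynced days, or a missing-data rule for steps. The lost-to-follow-up rule in Protocol Section 1.3 concerns the exit survey only.

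On wear, the intervention arm is told in Section 2.8 to wear the device daily ("instruct them to continue wearing it every day until the 9 weeks are finished (unless they are bathing, swimming, or sleeping"), and the control instruction in Section 2.7 is the same. Controls have a reminder subscription set up, and staff "allow the participant to choose the times they will receive reminders to wear-sync their Fitbit". For the intervention arm, Section 1.3 states: "Participants will receive 2-4 text messages per day including a daily status report and a link to view the race". Appendix D adds that further messages may come if a participant forgets to sync or wear the device, and that recorded, synced steps move the player along the route.

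**The concern.** A recorded step count equals walking only while the device is worn and synced. The protocol expects lapses in both arms, since it arranges prompts against them. The reward differs: an intervention participant who leaves the device off or unsynced makes no progress in the race, while a control loses nothing. MapTrek could therefore raise wear as well as walking.

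If unworn or part-worn days entered the model as zeros or low counts, and these were more common among controls, the fit would show higher steps in the intervention arm with no extra walking. A steady gap would load on the group term and a growing gap on group-by-day. Those are the two terms that answer the first objective. The participant intercepts and slopes would not remove a gap that differs by arm. A reader of the SAP cannot tell whether this could have happened.

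**Working it through.** The plan has no figure to reproduce: it gives no mean step count, wear rate, effect size or sample size. The inputs below are assumed unless marked.

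**Inputs**
- *g*: share of affected days in control minus share in intervention, -0.15 to +0.15.
- *m*: mean steps on a fully worn day, 5,000 to 7,000.
- *s*: share of the day's steps missed; 1 if the day is recorded as zero, 0.5 if half-captured.
- *d*: a person's true steps on worn days minus unworn days, 0 to 2,000.
- Follow-up: 8 race weeks (Protocol Section 1.3), taken as 56 days, days 0 to 55.
- Within-person SD: 3,000 assumed. The SAP says its prior bound of 25,000 is 4 to 5 times the largest plausible value, which implies an upper limit of 25,000/5 = 5,000 to 25,000/4 = 6,250.

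**Case 1: affected days enter as low counts.** Bias = g × m × s; a positive value favours MapTrek.
- s = 1: 0.05 × 5,000 = 250; 0.10 × 6,000 = 600; 0.15 × 7,000 = 1,050 steps/day.
- s = 0.5: 125; 300; 525.
- g = 0 gives 0; negative g gives the same sizes with the sign reversed.
- If the gap grows linearly from 0 over days 0 to 55, the false group-by-day slope is 250/55 = 4.5 to 1,050/55 = 19.1 steps/day per day (s = 1), or 2.3 to 9.5 (s = 0.5).

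**Case 2: affected days are absent.** Bias = -g × d.
- d = 0: 0.
- 0.05 × 1,000 = 50 to 0.15 × 2,000 = 300. The sign is opposite to Case 1 if unworn days are the less active ones, and the same if they are the more active ones.

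**Simulation check.** A frequentist mixed model with participant intercept and slope was fitted to simulated data with no day-of-week effect: 56 days, 100 per arm, 20% of control and 10% of intervention days affected, m = 6,000, 6 replicates.

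| How affected days arise or are coded | Bias, steps/day (SE) | Formula |
|---|---|---|
| Coded zero | +608 (43) | +600 |
| Half-captured | +317 (16) | +300 |
| Missing completely at random | -1 (3) | 0 |
| Missing by the person's usual level | -2 (10) | 0 |
| Missing on the person's less active days, d = 1,192 | -130 (9) | -119 |

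The same 10-point gap gives about +600 when coded as zero and about nothing in two of the three missing-day rows. A wear gap alone therefore does not make the group estimate inseparable from wear. The result depends on how the days were coded and why they were missing.

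**Would a valid-day cut-off help?** Suppose only step counts are available and days below a threshold are dropped, with gamma-distributed daily steps and m = 5,000 to 7,000.

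| SD | Full-wear days removed, 1,000-step cut | Full-wear days removed, 2,000-step cut | Half-captured days passing 1,000 |
|---|---|---|---|
| 3,000 | 0.1-2.9% | 1-13% | 87-99% |
| 5,000 | 4-18% | 12-33% | 67-88% |
| 6,250 | 9-28% | 20-42% | 58-80% |

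At SD 3,000 a 1,000-step cut leaves 86-98% of the part-wear bias and a 2,000-step cut leaves 59-83%. The cut misses most of what it is aimed at, and at the upper end of the SD range it discards a sizeable share of genuine days.

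**The case for a change.** The strongest case for acting is that the two ways of treating these days give materially different answers, that the SAP does not say which was used, and that the sponsor could settle it with one sentence and a table of recorded days by arm and week. All of that is true. The one-sided game reward is also in the protocol, and random effects do not protect against zero-coding.

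Three points limit it. First, both the fault and its direction are conjecture. The documents hold no wear data, and the asymmetry is modest: the wear instruction is identical, controls have a reminder set up for each participant, and the intervention arm's wear or sync messages are only possible ones. Second, the absence of a wear covariate is not a defect. Wear is measured after randomisation and may be affected by arm, so adjusting for it can introduce bias. Third, restricting to valid days conditions on that same variable and carries the Case 2 bias of 50 to 300 steps/day when non-wear follows that day's activity. Any threshold would also be chosen after the analysis, since the SAP is dated 6/7/2024 and written in the past tense. A rule based on worn time would be better than a step cut, but the protocol does not show that worn time was kept.

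**Conclusion.** No change to the plan follows. What stands is an unwritten coding detail in a short, retrospective SAP. It is the kind of gap analysts usually fill sensibly: a whole day with no data adds no row to a daily mixed model, and the participant intercept and slope then largely absorb non-wear that tracks a person's usual level. On that reading the bias is about zero, or 50 to 300 steps/day in either direction if a person's unworn days differ from their worn days by 1,000 to 2,000 steps.

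A large distortion, up to 1,050 steps/day, needs two things together: unworn days entered as zeros, and a wear gap of up to 15 points between arms. The documents support neither, and every figure rests on assumed wear gaps and step levels. Part-worn days could still carry 125 to 525 steps/day at gaps of 5 to 15 points, but a step threshold would not remove most of that at the assumed SD of 3,000. How such days were coded is useful context when the results are read; its absence from the SAP does not show the analysis to be wrong.

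### The SAP does not say which model contrast answers Objective 1, and its model leaves out age, sex and BMI, at some cost in precision

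*SAP*

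**What the plan says.** Objective 1 in Protocol Section 1.2 is to "Assess the effectiveness of VA MapTrek as a whole to increase steps per day in veterans compared to the control group". It gives no day or averaging window. Section 1.1 adds, as background, that veterans should first walk more and then keep up the higher level.

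The SAP's first paragraph restricts the analysis to data after the intervention began and states that "the baseline data was not used to estimate the model". It fixes the time origin: "We defined the start date of the intervention as Day 0 for all participants". On the model, it says: "We included fixed effects for day-of-week, days since the start of the intervention period, group indicator (Intervention Group versus Control Group), and an interaction". That last term is the group-by-days product. Participants have a random intercept and a random slope. The text then moves to priors and sampling. It gives no effect summary, interval level or decision rule.

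Baseline information exists. Age, sex and BMI are recorded at screening (Section 2.3), before the folder draw (Section 2.6). Both arms also wear the device from enrolment: "All consented participants will be provided with a Fitbit and instructed to wear it all day, every day for the next 9 weeks". The first of those weeks is the baseline week (Section 1.3).

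**The concern.** With an interaction in the model and time measured from Day 0, the group coefficient describes the first day of the race period only. Anyone looking for one number for Objective 1 could take the Day 0 gap, the average over the race weeks, the last-day gap or the slope difference. All come from the same fit and can differ materially. Because the plan chooses none of them, the choice can be made after the results are seen.

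The second issue is smaller. A random intercept accounts for repeated measures within a person, but it does not remove between-person variance from the arm comparison. Covariates known before assignment can remove part of it. The model has none.

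**Working it through.** The documents give no sample size, SD or target effect, so there is no planned figure to reproduce. The effect sizes, SDs and correlations below are assumptions.

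**1. Day 0 coefficient against period average**

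The modelled arm difference on day t is β_group + β_int × t. Its average over the window is β_group + (mean day) × β_int, so the Day 0 coefficient minus the average is −(mean day) × β_int. This is zero only when β_int is zero.

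Window: Section 1.3 describes 8 Monday-to-Saturday races. Including the Sundays between them gives 8 × 6 + 7 = 55 days (0-54), with mean day 27 and sum of squares about the mean 13,860. Eight full weeks would be days 0-55, with mean 27.5. The SAP does not state the last analysed day.

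For each assumed shape I fitted a least-squares line to the daily arm difference (days 0-54, complete data, assumed peak 1,000 steps).

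| Assumed effect | Line at Day 0 | Period average |
|---|---|---|
| Constant 1,000 | 1,000 | 1,000 |
| Linear fade, 1,000 to 0 | 1,000 | 500 |
| Linear build, 0 to 1,000 | 0 | 500 |
| 1,000 for 14 days, then 0 | 814 | 255 |
| Fade from 1,000, 14-day half-life | 772 | 352 |
| None for 14 days, then 1,000 | 186 | 745 |

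Example, fourth row: the average is 14,000/55 = 254.5. The slope is 1,000 × (91 − 14 × 27)/13,860 = −20.71. The Day 0 value is 254.5 + 27 × 20.71 = 813.6. In all six rows, Day 0 value + 27 × slope returns the true average, including where the shape is not linear. Days 0-55 change little (fourth row 803 against 250, fifth row 767 against 347). Every gap scales with the assumed 1,000.

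**2. Omitted pre-assignment covariates**

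Let τ be the between-person SD and σ the daily within-person SD. A participant's 55-day mean has variance τ² + σ²/55. If age, sex and BMI explain a share R² of τ², the level-contrast interval narrows by 1 − √[1 − R²τ²/(τ² + σ²/55)].

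Assumed: τ 2,000-6,250, σ 3,000-6,250, R² 0.05-0.20. The upper SD comes from the SAP's remark on its prior, "This upper bound of 25,000 was at 4-5x greater than the largest plausible values for these values": 25,000/5 = 5,000 to 25,000/4 = 6,250, if that bound applies to SDs.

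- R² 0.05, τ 2,000, σ 6,250: τ²/(τ² + σ²/55) = 0.849, so 1 − √(1 − 0.0425) = 2.1%.
- R² 0.20, τ 3,500, σ 3,000: the ratio is 0.987, so 1 − √(1 − 0.197) = 10.4%. At τ 6,250 it is 10.5%.

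**3. Baseline-week steps**

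With ρ the stability of the person's level (assumed 0.6-0.9), the correlation of the 7-day baseline mean with the follow-up mean is r = ρτ²/√[(τ² + σ²/7)(τ² + σ²/55)]. The interval narrows by 1 − √(1 − r²).

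- τ 2,000, σ 6,250, ρ 0.6: r = 0.357, narrowing 6.6%.
- τ 3,500, σ 3,000, ρ 0.9: r = 0.851, narrowing 47.4%.
- τ 6,250, σ 3,000, ρ 0.9: r = 0.884, narrowing 53.2%.

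The risk is that the baseline week itself differs by arm. The adjustment coefficient is b = ρτ²/(τ² + σ²/7), which is 0.25 to 0.87 over the same range. A 500-step arm shift in the baseline week that ended at Day 0 would move the adjusted estimate by about 125 to 436 steps and leave the unadjusted one unmoved. If the shift persisted in full, the unadjusted estimate would carry all of it and the adjusted one 0.13 to 0.75 of it.

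**The case against.** The model determines the arm difference on every day, so nothing is missing from it. The SAP describes finished work ("Statistical analysis was done using Bayesian mixed effects linear regression"), so any summary chosen now is as post hoc as the choice being criticised. The period average is also a reviewer's preference. It would hide the maintenance aim of Section 1.1, since linear fade and linear build both average 500. Much of this stands. The average needs the post hoc label and must appear beside the group-by-days term. What remains is that no contrast is named.

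A reader might infer that the trial's answer is wrong by hundreds of steps. The documents do not support that. They do not say that the Day 0 coefficient was used as the answer. The gap is zero under a constant effect and otherwise depends on an effect size they do not give.

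A reader might also infer that ignoring baseline biases the comparison, or that baseline steps should have been in the main model. Neither follows. Under random assignment, omitting a baseline covariate costs precision only. Leaving baseline-week steps out is defensible because participants know their arm before that week begins (Section 2.6). Control reminders start on the day of enrolment (Section 2.7), while the intervention enrolment steps list no matching subscription before the race (Section 2.8).

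Finally, the SAP places its 0-25,000 prior on the diagonal of a covariance matrix. Read literally as variances, this would cap the random-intercept SD at √25,000 ≈ 158 steps, and the existing level-contrast intervals could not be relied on. The correlation-type prior on the off-diagonals suggests that SDs were meant, but this needs confirming before the existing draws are used.

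**Conclusion.** The point holds in two parts and should be acted on.

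First, the contrast that answers Objective 1 is not named. The Day 0 coefficient differs from the period average by the mean day times the interaction: 500 steps for a linear fade or build of an assumed 1,000, and nothing for a constant effect.

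Second, omitting age, sex and BMI costs about 2-10% of interval width on level contrasts. This rests on an assumed 5-20% of between-person variance explained, which the documents neither support nor exclude. It introduces no bias.

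The possible gain from baseline-week steps, roughly 7-53%, illustrates the assumed SDs and does not bound the true gain. Their measurement after known assignment keeps that adjustment secondary. Confidence is medium, because every magnitude depends on assumed inputs.

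**What to change.** 1. From the existing draws, report the posterior of β_group + (mean calendar day of the analysed window) × β_int, with its credible interval, as the Objective 1 level effect. The multiplier is 27 for days 0-54 and 27.5 for days 0-55; state the window used. Show the group-by-days term beside it so that maintenance is visible, and label the choice post hoc. Cost: one derived quantity and no re-fit, provided the draws were kept and the 25,000 bound is confirmed to apply to SDs.
2. Report the same contrast from a second model that adds age, sex and BMI, labelled post hoc. Cost: one extra fit with fields already collected.
3. Optionally, as a supportive post hoc analysis, add centred mean steps from one common 7-day window before Day 0, since Section 1.3 lets early enrollees wear the device longer. Include a rule for missing or unworn days, and show baseline steps and wear days by arm. Cost: one extra fit plus those two definitions.

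The existing unadjusted model stays primary.
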